## SYNOPSIS

**Summary:** Despite a gradual improvement in their overall survival over the past decade, approximately 75% of women with Stage IIIC ovarian cancer who achieve a complete clinical response will relapse as will 50% of those achieving pathologic complete response at a median time of 18-24 months. Phase III studies of both maintenance and consolidation therapeutic interventions have not translated into an overall survival advantage. Preliminary studies of immunotherapy in patients with ovarian cancer suggest target accessibility (potential immunogenicity) to immune mediated approaches. In an effort to overcome limitations of immunostimulatory cancer vaccines, we designed a novel autologous whole cell vaccine, Vigil™ formerly known as FANG™, incorporating the rhGMCSF transgene and the bifunctional shRNAfurin (to block proprotein conversion to active TGFβ1 and β2) to 1) address the inability to fully identify cancer associated antigens, 2) effect antigen recognition by the immune system (i.e. antigen→immunogen), 3) enhance effector potency, and 4) subvert endogenous cancer-induced immune resistance.

A Phase I assessment of Vigil™ vaccine in 33 advanced solid tumor patients (1 of them being a pediatric patient 15 years of age) receiving ≥1 vaccination (at a dose of  $1.0 \times 10^7$  or  $2.5 \times 10^7$  cells/injection/month for a maximum of 12 vaccinations) demonstrated safety of the Vigil™ vaccine. Furthermore, proof of principle was established in the manufactured vaccines with increased mean GMCSF expression post-transfection to  $1135 \text{ pg}/10^6 \text{ cells/ml}$  and knockdown of furin, TGFβ1 and TGFβ2 at 78%, 93%, and 95%, respectively). In addition, although a Phase I study, the data suggested an overall survival benefit.

Given the preliminary Phase II evidence of prolongation of time to relapse in randomized Vigil™ vs. No Vigil™ treated patients ( $p=0.005$ ), as of this amendment all patients screening for enrollment into the main portion of the trial (including those who previously had tumor tissue harvested), will receive Vigil™ vaccine and will no longer be randomized. An extensive Phase II/III protocol is designed to more definitively assess benefit. Additional safety data in ovarian cancer patients receiving  $1 \times 10^7$  cells/ID injection on a monthly basis (maximum 12) is required.

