### 1.3 Immune Function Capacity in Ovarian Cancer Patients

The majority of women diagnosed with cancer of the ovary present in advanced stage (Jemal, Siegel et al. 2009) with 5-year survival rates of 46.7% for Stage IIIa, 41.5% for Stage IIIb, and 32.5% for Stage IIIc (Heintz, Odicino et al. 2006). Despite a gradual improvement in overall survival over the past decade, approximately 75% of the women with Stage III/IV ovarian cancer who achieve a complete clinical response will relapse, as will 50% of those achieving pathologic complete response at a median time of 16-24 months depending on risk factors (Gadducci, Sartori et al. 1998; Markman, Liu et al. 2003; Gadducci, Cosio et al. 2005). Phase III studies of both maintenance and consolidation therapeutic interventions have not had an impact on overall survival (Mei, Chen et al. ; Foster, Brown et al. 2009; McGuire 2009; Pecorelli, Favalli et al. 2009). It is therefore pertinent that expression of all three immunosuppressive TGF $\beta$  isoforms is increased in ovarian tumor as compared with normal ovarian tissue (Henriksen, Gobl et al. 1995; Bristow, Baldwin et al. 1999) with significant increases in TGF $\beta$ 1 in both primary (2.9 fold;  $p \leq 0.002$ ) and recurrent (4.4 fold;  $p \leq 0.002$ ) ovarian cancer (Bristow, Baldwin et al. 1999). Secreted TGF $\beta$  from ovarian cancer cells generate immunosuppressive Treg cells (CD4+CD25+) from peripheral CD4+CD25- cells (Li, Ye et al. 2007). Both Treg tumor infiltration as

well as the granzyme B+/FOX3p+ ratio are associated with outcome in those patients treated with neoadjuvant chemotherapy (Polcher, Braun et al.). The contribution of optimal surgical cytoreductive surgery to prognosis may be due, in part, to the associated reduction in circulating Tregs (Napoletano, Bellati et al. 2009). In a recently described transgenic LSL-K-rasG12D/+ p53loxP/loxP murine model of induced metastatic ovarian cancer in the setting of a mature immune system (Scarlett, Rutkowski et al.), a shift in dendritic cell phenotype from immunostimulatory to immunosuppressive was shown to be due to tumor-cell derived TGF $\beta$ 1 and PGE2 both of which were found to be secreted at high levels in advanced tumors (Scarlett, Rutkowski et al.). Further, TGF $\beta$  has been linked to the emergence of cisplatin resistance (Li, Balch et al. 2009).

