## 4.0 STUDY DESIGN

### 4.1 Design

This is a Phase II open-label trial of maintenance Vigil™ autologous tumor cell vaccine. Tumor will be harvested at the time of surgical debulking (standard of medical care). Subsequently, patients achieving clinical CR following primary surgical debulking and doublet chemotherapy will be stratified for i) surgical stage (Stage IV or suboptimal debulking (>1 cm residual) Stage III disease versus Stage III patients with optimal debulking (<1 cm residual)) and ii) post-op chemotherapy, pre-vaccine CA-125  $>10 \leq 20$  U/mL versus  $0 \leq 10$  U/ml, then randomized 2:1 (Note: patients with Stage IIIC ovarian cancer will be additionally evaluated as a subset using descriptive statistics only). Patients will receive  $1.0 \times 10^7$  cells / intradermal injection of gene transfected autologous tumor cells, Vigil™, once a month for up to 12 doses as long as sufficient material is available. Enough harvested tissue to provide a minimum of 4 monthly injections will be required for entry into the study. These patients will be managed in an outpatient setting. Hematologic function, liver enzymes, renal function and electrolytes will be monitored monthly. Immune function analysis including

ELISPOT analysis of cytotoxic T cell function to autologous tumor antigens will be monitored at ( $\leq$ 24 hours before) tissue harvest,  $\leq$ 24 hours before the first cycle of chemotherapy (post debulking),  $\leq$ 24 hours before the third cycle of chemotherapy (post debulking), baseline (screening), prior to Vigil™ injection Months 2, 4, 6 and at EOT. The dates of the last dose of chemotherapy and the administration of Vigil™ vaccine #1 will be recorded.

Treatment will be continued until disease recurrence or exhaustion of the patient's vaccine supply. If  $\geq$  Grade 2 toxicity by NCI Common Toxicity Criteria (excluding Grade 2 fever  $\leq$  24 hours and Grade 2 and 3 injection site reactions) develops related to study treatment the vaccine dose will be reduced by 50% and continued on a monthly basis. If a single patient develops  $\geq$  Grade 3 toxicity (other than injection site reaction) related to study treatment the trial will be placed on hold for reevaluation of design in discussion with FDA. During this hold, no new subjects will initiate dosing, but subjects already being dosed may continue dosing as scheduled if deemed clinically appropriate by the PI.

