### 5.2 Inclusion Criteria

Patients will be eligible for tissue procurement for the Vigil™ vaccine manufacturing process if they meet all of the following criteria:

1. Presumptive Stage III/IV papillary serous or endometrioid ovarian cancer.
2. Per Amendment #8, treatment naïve, high risk ovarian cancer will no longer be stratified, but the following information will be collected:
  - a. Stage IV or suboptimal ( $>1$  cm residual) Stage III disease versus Stage III patients with optimal ( $\leq 1$  cm residual) disease,
  - b. CA-125  $\leq 10$  U/ml versus CA-125 greater than 10 but less than or equal to 20 U/ml
  - c. IP chemotherapy versus IV chemotherapy
3. Availability of "golf-ball" size 10-30 grams tissue at time of primary surgical debulking.

4. ECOG performance status (PS) 0-2 prior to tumor debulking laparotomy.
5. Ability to understand and the willingness to sign a written informed consent document for tissue harvest.

Patients will be registered for inclusion in this study if they meet all of the following criteria:

1. Histologically confirmed Stage III/IV papillary serous or endometrioid ovarian cancer.
2. Clinically defined CR (no cancer related symptoms, normal physical examination and CT scan abdomen/pelvis and CXR, and CA-125  $\leq 20$  U/ml) following completion of primary surgical debulking. Patients enrolled must complete at least 5 but no more than 6 cycles platinum/taxane adjuvant or interval debulking + chemotherapy (or chemotherapy as per recommendations of NCCN guidelines, category 1 (IP chemotherapy included)). (Patients who complete surgery/chemotherapy with a CA-125  $> 20$  U/mL pre-registration have the option of being followed up to 2 months if serial CA-125 values continue to decrease at a rate of CA-125 decrease of  $\geq 50\%$  per month.)
3. Successful manufacturing of 4 vials of Vigil™ vaccine.
4. Recovered from all clinically relevant toxicities related to prior protocol specific therapies (including neuropathy to  $\leq$ Grade 2).
5. ECOG performance status (PS) 0-1.
6. Normal organ and marrow function as defined below:

Absolute granulocyte count	$\geq 1,500/\text{mm}^3$
Absolute lymphocyte count	$\geq 200/\text{mm}^3$
Platelets	$\geq 75,000/\text{mm}^3$
Total bilirubin	$\leq 2 \text{ mg/dL}$
AST(SGOT)/ALT(SGPT)	$\leq 2x$ institutional upper limit of normal
Creatinine	$< 1.5 \text{ mg/dL}$

7. Patients must be off all "statin" drugs for  $\geq 2$  weeks prior to initiation of therapy.

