## 13.0 DATA EVALUATION

### 13.1 Statistics and Estimated Sample Size

The primary objective of this study is to investigate whether maintenance Vigil™ vaccine after a clinically defined complete response to induction platinum/paclitaxel chemotherapy results in prolonged time to recurrence (TTR) compared with standard of care observation. TTR was used for the purpose of sample-size estimation. Based on prior published experience (Markman, Liu et al. 2003), the median RFS after a clinical complete response to induction therapy for the control arm was estimated to be approximately 16 months for those with stage IV or suboptimal (> 1 cm residual) stage III disease and 24 months for stage III patients with optimal (< 1 cm residual) disease. Given an average RFS of 24 and 16 months, respectively, a 10% increase in RFS (i.e. TTR) would provide adequate statistical power to support expanding the study (Table 6). This analysis was performed using a statistical power calculator (<http://www.dssresearch.com/KnowledgeCenter/toolkitcalculators/statisticalpowercalculators.aspx>) to conduct a 1-tail test of a sample average in comparison to the historical value, a standard deviation of 1.0, and an alpha error level of 5%. In order to expand the protocol treatment base and increase the rate of accrual while maintaining the objectives of the protocol, the study, which was initially limited to patients with stage IIIC ovarian cancer, is being expanded to patients with Stage III/IV disease. In the SEER database: 1988-2001(Kosary 1988-2001), women with Stage IIIC disease comprised 19.4% of the ovarian cancer population; those with Stage III inclusive, 35.3%; and those with Stage IV, 31.7%. Thus, the eligibility expansion increases the base catchment population from 19.4% of women with ovarian cancer to 67% of which only a subset will meet protocol criteria.

In the completed Phase I study of Vigil™ vaccine in patients with solid tumors experiencing progressive disease following prior therapy, 50% of patients with serial assessments (n=18) demonstrated conversion from  $\gamma$ IFN ELISPOT

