negative to positive by Month 4 (Senzer N 2012). The percent  $\gamma$ IFN ELISPOT conversions and the timing thereof will be recorded in the current patient population of patients with minimal or no residual disease using descriptive statistics to assess the hypothesis that there is an inverse relationship between tumor volume and immune responsiveness based in part on the quantitative relationship between tumor volume and the production of immunosuppressive factors.

Although all patients will be evaluated for RFS, subgroup analyses will be separately performed on patients with negative ELISPOT at baseline and those with positive ELISPOT at baseline.

**Table 6:** Statistical Power of 2:1 Randomization Trial per Surgical Stage Stratification Group (1 tailed t test)

Surgical Stage Stratification	Vigil™ Vaccine (TTR in months)	Observation Control (TTR in months)	Power	n
Stage III patients with optimal (< 1 cm residual)	26.4	24	1.0	30
Stage IV or suboptimal (> 1 cm residual) stage III disease	17.6	16	1.0	30

Exploratory analysis of two Phase III studies (D9901 and D9902) with the recently FDA approved Provenge documented prolonged survival benefits in Provenge-treated prostate cancer patients (25.9 months vs. 21.4 months and 25.8 vs. 21.7 months, respectively). Supporting our clinical objective, patients who subsequently received docetaxel experienced a median survival of 34.5 months compared to 25.4 months in patients treated with placebo followed by docetaxel. Descriptive statistics will be employed to format the response rates and response durations to 2nd line therapy in patients that relapse in both FANG™ and observational groups.

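### Table 6's power of 1.0 for a 10% longer TTR rests on an unsupported SD of 1.0; with exponential recurrence times the power is about 8–17%

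*Combined protocol and SAP*

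**What the plan says.** Section 13.1 sets a comparative primary aim: longer time to recurrence (TTR) on Vigil than under standard-of-care observation. It takes control medians of 16 months (stage IV or suboptimal stage III) and 24 months (optimal stage III) from a published trial, then restates them as means: "Given an average RFS of 24 and 16 months, respectively". It concludes that "a 10% increase in RFS (i.e. TTR) would provide adequate statistical power to support expanding the study". The calculation is described as a "1-tail test of a sample average in comparison to the historical value, a standard deviation of 1.0, and an alpha error level of 5" per cent.

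Table 6 gives power 1.0 with n = 30 in each stratum, for 26.4 v 24 and 17.6 v 16 months. Its caption describes another test: "Statistical Power of 2:1 Randomization Trial per Surgical Stage Stratification Group (1 tailed t test".

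The design text is split. The Synopsis says that patients now screening "will receive Vigil™ vaccine and will no longer be randomized", and section 5.2 says "Per Amendment #8, treatment naïve, high risk ovarian cancer will no longer be stratified". Section 4.1 still has patients stratified and "then randomized 2:1", as does the Synopsis methodology, and section 5.1 still says that about 50 patients will be randomized.

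**The concern.** TTR is a time-to-event endpoint, but the power comes from a test of means with an SD of 1.0. No unit, source or rationale is given for that SD; months is the natural reading. No event count, follow-up time or censoring enters.

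An SD of one month around 24 or 16 months means that about 95% of patients recur within two months either side of the average. Section 1.3 says that "approximately 75% of the women with Stage III/IV ovarian cancer who achieve a complete clinical response will relapse", so about 25% do not. The two statements are not compatible.

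This is the only sample-size justification in the document. A stated power of 1.0 tells the reader that failing to show a 10% gain would rule one out. If power is really 8–17%, a true 10% gain would be missed more than 80% of the time, and the primary result would be misread.

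**Working it through.** **Inputs.** From section 13.1 and Table 6: one-sided alpha 5% (z = 1.645), SD 1.0, n = 30 per stratum, differences of 2.4 and 1.6 months, 2:1 allocation. From section 5.1: about 50 patients. From section 1.3: about 75% relapse.

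**Step 1: reproduce Table 6.** One-sample power is Φ(δ√n/SD − 1.645).
- 24-month stratum: 2.4 × √30 / 1 = 13.1; power 1.000.
- 16-month stratum: 1.6 × √30 / 1 = 8.8; power 1.000.
- Two-sample t test, 20:10, SD 1.0: 0.99999 and 0.991.

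The table is therefore right for its inputs under either reading of the test.

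**Step 2: how small must the SD be?** For 80% power at n = 30 (t tests), it can be at most 5.2 and 3.4 months (one-sample) or 2.4 and 1.6 months (20:10), for the 24- and 16-month strata. Compare the SDs of Weibull times with these medians:

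| Weibull shape | SD, median 24 | SD, median 16 |
|---|---|---|
| 1 (exponential) | 34.6 | 23.1 |
| 2 | 13.4 | 8.9 |
| 3 | 8.8 | 5.9 |

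An SD of 1.0 needs a shape of about 30 (median 24) or 20 (median 16).

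**Step 3: event-based power.** A 10% longer median with exponential times is a hazard ratio of 1/1.1 = 0.909, and ln 1.1 = 0.0953. With d events and Weibull shape k,

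power = Φ(k × 0.0953 × √(d·w) − 1.645),

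where w = (2/3)(1/3) = 2/9 for a 2:1 comparison and w = 1 against a fixed historical value. Example, k = 1 and d = 30: 2:1 gives Φ(0.246 − 1.645) = 8.1%; historical gives Φ(0.522 − 1.645) = 13.1%.

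The event counts are 30 (one stratum, all with events), 22.5 (75% of 30), 50 (all patients) and 37.5 (75% of 50).

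| Shape k | Comparison | d = 22.5 | 30 | 37.5 | 50 |
|---|---|---|---|---|---|
| 1 | 2:1 | 7.6% | 8.1% | 8.5% | 9.2% |
| 1 | historical | 11.6% | 13.1% | 14.4% | 16.6% |
| 2 | 2:1 | 11.1% | 12.5% | 13.7% | 15.6% |
| 2 | historical | 22.9% | 27.4% | 31.6% | 38.3% |
| 3 | 2:1 | 15.7% | 18.2% | 20.6% | 24.5% |
| 3 | historical | 38.6% | 46.9% | 54.2% | 64.7% |

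An exact one-sample exponential test gives 14.0% at 30 events and 17.6% at 50, close to the formula.

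**Step 4: match to the current mixed design.** The number already randomized is not given. Assume R of 50 were randomized 2:1 and the rest all receive vaccine, with 75–100% having events and exponential times:

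| R | On vaccine | Power, randomized patients | Power, vaccine v historical |
|---|---|---|---|
| 15 | 45 | 6.8–7.1% | 13.8–15.7% |
| 30 | 40 | 7.6–8.1% | 13.1–14.9% |
| 50 | 33.3 | 8.5–9.2% | 12.1–13.7% |

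**Step 5: what could be detected.** Events for 80% power at a hazard ratio of 0.909 are (1.645 + 0.842)²/(0.0953² × w): about 681 (historical) or 3,063 (2:1). In reverse, at 37.5–50 events the hazard ratio detectable with 80% power is exp(−2.487/√(d·w)): about 0.42–0.47 if all were randomized 2:1, and 0.67–0.70 if all were in one arm against a fixed historical value.

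**The case against.** Several points on the other side are fair.

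- The power of 1.0 does not need an SD of exactly 1.0. One-sample power still prints as 1.0 to one decimal (0.95 or more) for SDs up to about 4.0 months (24-month stratum) or 2.7 months (16-month stratum). This stands, but those SDs are also implausibly small.
- The documents give no dispersion data, so 8–17% depends on the exponential shape. The 17% also needs all 50 patients to have events, pooled across strata. At n = 30 the range is 8–14%. This stands too, which is why shapes 2 and 3 are shown; they do not rescue the claim.
- Section 13.3 counts death before recurrence as an event, and section 1.3 gives no follow-up horizon. So 75% relapsing is not the same as 75% having events. The 75–100% range covers this.
- A log-rank simulation (20:10, exponential) gave about 10% rather than 8.1%. The same test rejected 7.0% of the time under the null, so it is not an exact 5% test and is not relied on here.
- Table 6 looks like a remnant of the randomized design. Section 3.1 states the primary objective without a comparator, the Synopsis already reports p = 0.005 for randomized patients, and definitive assessment is left to a later protocol. But section 13.1 is current text, keeps the comparative aim and has no replacement. A small p-value may reflect a much larger effect; it neither supports an SD of 1.0 nor makes a 10% gain detectable.

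**Conclusion.** The concern holds. Table 6 is computed correctly from an SD that the plan does not support and that its own relapse figure contradicts. For a 10% longer median at one-sided 5%, power is about 8–9% (2:1) or 13–17% (fixed historical value) with exponential times and 30–50 events. It stays below 80% in every Weibull scenario tried, the highest being 64.7%. The exact value cannot be fixed from the documents, because it depends on the shape of the distribution, the number of events and the comparison intended. The historical figures are on the generous side, since they treat the approximate 16- and 24-month medians as known without error.

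Two lesser faults sit alongside: the text and the caption name different tests, and the strata total 60 against about 50 planned. The second does not drive the power; at n = 25 the one-sample figure is still 1.000. A TTR gain near or below 10% cannot be interpreted as section 13.1 implies.

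**What to change.** Keep the sample size. Then:

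1. Withdraw the power of 1.0 and the sentence claiming adequate power for a 10% gain.
2. State which comparison applies after Amendment #8: patients already randomized (Vigil v observation), vaccine-treated patients v the historical medians, or both. Reconcile the no-longer-randomized and no-longer-stratified statements (Synopsis, section 5.2) with the randomization wording (Synopsis methodology, sections 4.1 and 5.1).
3. Replace Table 6 with a time-to-event calculation for that comparison, using its actual number of patients and expected events. State the assumed distribution and the fraction expected to have an event.
4. Report the low power for a 10% gain and the hazard ratio detectable with 80% power. The values in Step 5 of the working are illustrations for the two pure designs, not for the mixed one.
5. Make the table's n agree with about 50.

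The cost is a far less favourable stated power, a few hours of statistician time, and possibly a formal amendment under section 7.5. No extra patients or visits are needed.

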**Methodology:**

This is a Phase II open-label trial of Vigil™ autologous tumor cell vaccine. Tumor will be harvested at the time of surgical debulking (standard of medical care).

Patients achieving clinical complete response (CR) following primary surgical debulking and doublet chemotherapy will be stratified for i) surgical stage (Stage IV or suboptimal debulking (>1 cm residual) Stage III disease versus Stage III patients with optimal debulking (<1 cm residual)) and ii) post-operative chemotherapy, pre-vaccine CA-125 of greater than 10 but less than or equal to 20 U/mL versus 0≤10 U/ml then randomized 2:1 (Note: patients with Stage IIIC ovarian cancer will be additionally evaluated as a subset using descriptive statistical endpoint only). Patients will receive  $1.0 \times 10^7$  cells / intradermal injection of gene transfected autologous tumor cells, Vigil™, once a month for up to 12 doses as long as sufficient material is available. A minimum harvest aliquot to produce 4 monthly injections will be required for entry into the study. These patients will be managed in an outpatient setting. Hematologic function, liver enzymes, renal function and electrolytes will be monitored monthly. Immune function analysis including ELISPOT analysis of cytotoxic T cell function to autologous tumor antigens will be monitored at (≤24 hours before) tissue harvest, ≤24 hours before the first cycle chemotherapy (post debulking), ≤24 hours before the third cycle chemotherapy (post debulking), baseline (screening); prior to Vigil™ injection at Months 2, 4, 6 and EOT. CA-125 will be monitored at baseline, every month for the first year, every 3 months ± 2 weeks for the second and third year.

**Number of Patients:** Approximately fifty (50) patients with high risk Stage III/IV ovarian cancer.

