## 5.0 STUDY POPULATION

### 5.1 Sample Size

Approximately fifty (50) treatment naïve patients with high risk Stage III/IV ovarian cancer who achieve clinical CR following surgical debulking and chemotherapy will be randomized in this trial.

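### No primary TTR test or success rule is named: the only test described is a one-tailed 5% t test in each surgical-stage group, it ignores CA-125, and its sample sizes add to 60 against about 50 planned

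*Combined protocol and SAP*

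**What the plan says.** Section 13.1 states one primary question: does Vigil maintenance after a clinical complete response lengthen TTR relative to observation? Section 3.1 words the primary objective more loosely, as assessing TTR after vaccination.

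A test appears only in the sample-size material of Section 13.1. A 10% gain "would provide adequate statistical power to support expanding the study". A web calculator was used "to conduct a 1-tail test of a sample average in comparison to the historical value", with "a standard deviation of 1.0, and an alpha error level of 5" per cent. Table 6, headed "Statistical Power of 2:1 Randomization Trial per Surgical Stage Stratification Group (1 tailed t test", has two rows: 26.4 against 24 months and 17.6 against 16 months, each with n = 30 and power 1.0. Section 13.1 adds that all patients will be evaluated for recurrence-free survival (RFS), with subgroup analyses by baseline ELISPOT, but gives no method. Sections 13.3 to 13.5 define TTR, time to treatment failure and survival without naming a test or model.

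The synopsis Methodology and Section 4.1 stratify by surgical stage and by CA-125 ("pre-vaccine CA-125 of greater than 10 but less than or equal to 20 U/mL" against 10 or less), then randomise 2:1. The synopsis Summary says new patients are no longer randomised. Criterion 2 in the synopsis and in Section 5.2 says that "high risk ovarian cancer will no longer be stratified, but the following information will be collected". Section 5.1 plans "Approximately fifty (50) treatment naïve patients with high risk Stage III/IV ovarian cancer" and still describes them as being randomised.

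**The concern.** One question needs one answer. Two separate group tests can disagree, and the plan does not say what then counts as support for expanding the study. An unwritten rule can be chosen after the results are known. That risk is larger than usual here: the trial is open-label, and according to the synopsis Summary a randomised comparison (p = 0.005) has already been seen and has changed the design.

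CA-125 was used to balance the arms for randomised patients, but Section 13 does not mention it. An analysis that omits a stratification factor does not follow the design that produced the data. A t test on average TTR also has no stated way of handling patients who have not recurred.

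**Working it through.** **1. The plan's own figure.** Inputs from Section 13.1 and Table 6: differences of 2.4 and 1.6 months, SD 1.0, one-sided 5% (z = 1.645), n = 30 read as 20 Vigil and 10 control.

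- Standard error = 1.0 × √(1/20 + 1/10) = 0.387.
- Optimal Stage III: 2.4/0.387 = 6.20. Power = Φ(6.20 - 1.645) > 0.9999.
- Stage IV or suboptimal Stage III: 1.6/0.387 = 4.13. Power = Φ(4.13 - 1.645) = 0.994 (0.991 with the noncentral t).
- Read instead as one sample of 30 against a fixed value, the second row gives Φ(1.6 × √30 - 1.645) ≈ 1.0.

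The stated 1.0 reproduces, to the precision shown, under both readings. It therefore cannot show which test was meant.

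**2. Error of two group tests.** The groups contain different patients, so the tests are taken as independent.

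| Rule for success | Formula | One-sided error |
|---|---|---|
| Either group | 1 - (1 - 0.05)² | 9.75% |
| Both groups | 0.05² | 0.25% |
| One combined test | by construction | 5% |

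A simulation of 200,000 pairs of null t tests (20 against 10) gave 9.72% for either group and 0.25% for both.

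**3. Sample size.** Table 6 gives 30 + 30 = 60; the synopsis and Section 5.1 give about 50. If the 50 are assumed to split equally, with 17 Vigil and 8 control in each group, the same formula gives more than 0.999 and 0.982. Under the plan's own assumptions the mismatch barely moves the power. It is an inconsistency to correct, not a hidden loss of power.

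**4. Passages that conflict.**

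- Type of comparison: the Section 13.1 text has a sample average against a historical value; Table 6 has a 2:1 randomised t test.
- Stratification: the synopsis Methodology and Section 4.1 keep it; criterion 2 in the synopsis and in Section 5.2 removes it.
- Randomisation: the synopsis Methodology and Sections 4.1 and 5.1 keep it; the synopsis Summary stops it for new patients.

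**The case against.** The strongest reply is that Table 6 is a power table and Section 13.1 says TTR served for sample-size estimation. Nothing says that two t tests will be run on the trial data. That stands: the per-group tests are inferred to be the analysis because no other test is described. The accurate finding is that no primary analysis is specified.

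A reader might infer that the trial's false-positive rate is nearly 10%. The documents do not support this. The 9.75% needs a rule that success in either group suffices, and no section adopts one; under the opposite rule the error is 0.25%.

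A reader might also infer that no overall analysis is intended. The statement that all patients will be evaluated for RFS points the other way, although it supplies no method.

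It can fairly be said that separate 16- and 24-month benchmarks already allow for case mix by surgical stage. They do, and they should be kept for any historical comparison. It is also fair that the CA-125 point has force only for patients who were actually stratified and randomised. For later patients the current criteria merely collect it.

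**Conclusion.** The point holds as an omission with inconsistencies around it. Section 13 names no primary TTR test, no way to combine the two surgical-stage groups and no success rule, and it leaves out a factor used to stratify the randomised patients. Conditional on the Table 6 tests being the analysis and being independent, the one-sided error lies anywhere from 0.25% to 9.75%, depending on a rule the plan does not give. The sample size in Table 6 (60) does not match the plan (about 50), and the text and the table heading describe different comparisons. These should be settled before TTR is analysed.

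**What to change.** - **Primary test.** In Section 13.1, name one TTR test at one-sided 5%: a log-rank test, with a Cox estimate, in the randomised patients, stratified by surgical stage and CA-125. State that this result alone decides whether expansion is supported.
- **Time origin.** Section 13.3 starts TTR at first dose, which observation patients do not have. Define an origin that applies to both arms, such as randomisation.
- **Supportive results.** Report the surgical-stage groups and the Vigil-only patients as supportive or descriptive. Compare the Vigil-only patients with the stage-specific 16- and 24-month benchmarks, not one pooled figure. With exponential times and an assumed 30% to 70% optimally debulked, a pooled median would run from 18.0 to 21.2 months. That 3.2-month range exceeds the 1.6- and 2.4-month target effects.
- **Table 6.** Restate n to match about 50 and recompute power for the test named.
- **Consistency.** Choose between the historical and the randomised description in Section 13.1. Reconcile the synopsis Methodology and Sections 4.1 and 5.1 with the synopsis Summary and criterion 2.

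The stratification data are already collected, so the cost is mainly rewriting, with three limits. Success can no longer be claimed from one stage group alone. The strata may be sparse: the number randomised is not given, but even with all 50 there would be 50/4 = 12.5 patients per stratum on average, about 4 of them controls, so a rule for collapsing strata should be set in advance. And naming the test now does not undo the look at the randomised data already reported.
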